## **6.7 Rule of exclusion criteria of analysis sets**

The following table provides the protocol deviations (PD) and other criteria leading to partial or complete exclusion from analyses sets

[figure not shown]
Deviation ID	Description of Deviation
Deviations leading to exclusion from all analyses sets	
INCL01A	Informed consent not obtained
EXCL22A	Patient with custodial sentence. Do not have permanent residence or detained under local mental health legislation/regulation
Deviations leading to exclusion from RAN, FAS, PPS ██████████ analysis set	
OTH05A	Patient received study drug but was not randomized
Deviations leading to exclusion from FAS, PPS, Safety ██████████ analysis set	
OTH04A	Patient randomized but did not receive study drug
Deviations leading to exclusion from FAS and PPS	
OTH03A	Patient Randomized more than once in this study or randomized in another study
Deviations leading to exclusion from PPS	
INCL02A	Age < 12 years or > 75 years or missing
INCL03A	No documented diagnosis of Asthma for at least 3 months prior to Visit 1
INCL04A	Patients who are not treated with low dose ICS, with or without controller (ie, LABA, Leukotriene Receptor Antagonist (LTRA) at stable dose for at least 1 month (=30 days) prior to Visit 1
INCL05A	Adult patients with ACQ-7 score < 1.5 at visit 101 and/or visit 102
INCL06A	Adolescent patient on ICS only (without LABA), have ACQ -7 < 1.5 at visit 101 and/or visit 102
INCL06B	Adolescent patient on ICS+LABA have ACQ-7 score < 1 or >= 1.5 at visit 101
INCL06C	Adolescent patient on ICS+LABA have ACQ-7 score < 1.5 at visit 102
INCL07A	Pre Bronchodilator FEV1 < 60% or >= 90% of predicted normal after withholding bronchodilator both at visit 101 and 102
INCL08A	Patients for whom increase in FEV1 < 12% and/or < 200 ml within 30 minutes after administration of 400 microgram salbutamol/360 microgram albuterol (or equivalent dose) at Visit 101
INCL08B	Patient has not achieved an acceptable spirometry result does not have historical reversibility
INCL08C	Patient has not achieved assessments according to ATS/ERS criteria
EXCL01A	Patients who have smoked or inhaled tobacco products (including electronic cigarettes) within 6 months prior to visit 1
EXCL01B	Patient has a smoking history of >= 10 pack years or missing
EXCL02A	Adults: who had an asthma attack or exacerbation requiring systemic steroids or hospitalization or emergency room visit within 6 weeks of visit 1
EXCL02B	Adults: who had an asthma attack or exacerbation requiring systemic steroids or hospitalization or emergency room visit between visit 1 and 102

Deviation ID	Description of Deviation
EXCL02C	Adolescents: who had an asthma attack or exacerbation requiring systemic steroids or hospitalization or emergency room visit within 6 months prior to visit 1
EXCL02D	Adolescents: who had an asthma attack or exacerbation requiring systemic steroids or hospitalization or emergency room visit within: between Visit 1 and 102
EXCL03A	History of Intubation for severe asthma attack or exacerbation
EXCL05A	Patients with respiratory tract infection or asthma worsening between Visit 1 and Visit 102
EXCL05B	Patients with respiratory tract infection or asthma worsening within: 4 weeks prior to visit 1
EXCL06A	Clinically significant oropharyngeal candidiasis at Visit 102 or earlier, with or without treatment.
EXCL07A	Patient with chronic condition affecting upper respiratory tract (eg. chronic sinusitis)
EXCL08A	Patient have a medical history of chronic lung diseases other than asthma
EXCL11A	Other investigational drugs used within 30 days of visit 1 or 5 half lives or untill return of baseline pharmacodynamic effect whichever is longer.
EXCL21A	Patient on Maintenance Immunotherapy (desensitization) for allergies less than 3 months prior to Visit 101
EXCL21B	Patient on Maintenance Immunotherapy for allergies more than 3 months prior to Visit 101 but expected to change therapy throughout the study
EXCL21C	Monoclonal antibodies: IgE inhibitors and other asthma related biologics (e.g. omalizomab) IL-5 inhibitors (e.g. mepolizomab) taken within 4 months prio to run-in 101.
EXCL23A	Patient associated with any member of study team
EXCL24A	Patient unable to use the dry powder inhalers
EXCL25A	Patient has history of alcohol or other substance abuse since last 10 years
EXCL34A	LAMA taken less than 3 months prior to Visit 101
COMD09A	Parenteral or oral corticosteroids taken within 4 weeks prior to run in 101
COMD10A	Intra-muscular depot corticosteroids taken within 3 months prior to Run in 101
COMD12A	Xanthines taken within 7 days prior to Run In 101
COMD13A	Systemic mast cell stabilizers taken within7 days prior to Run in visit 101
OTH01A	Patient not having correct run in medication (i.e. 100mcg accuhaler or 125 mcg via MDI inhaler) or dose equivalent
OTH07A	Patient took study treatment not as per protocol (i.e not inhaled the study medication)
OTH12A	Compliance failure of the patient influencing the safety and efficacy data as per investigator judgement
OTH14A	Patient receiving investigational drug other than study drug during the course of the study
COMD02A	SAMA taken less than 8 hours prior to visit 101
COMD03A	Fixed combinations of $\beta$ 2-agonists and inhaled corticosteroids taken within 48 hours prior to Visit 101

Deviation ID	Description of Deviation
COMD04A	Fixed combinations of short-acting $\beta$ 2-agonist and short-acting anticholinergic taken within 8 hours prior to Visit 101
COMD05A	Leukotriene Receptor Antagonist (LTRA) and leukotriene synthesis inhibitors taken within 7 days prior to Run-in (Visit 101)
COMD06A	LABA b.i.d taken within 48 hours prior to visit 101
COMD07A	LABA o.d continuing at visit 1
COMD08A	Short Acting B2 Agonist, other than rescue medication is continuing after visit 1
WTH01A	Patient still on study treatment even after having 1 severe asthma exacerbation requiring treatment with systemic corticosteroids or hospitalizations
WTH06A	Blind broken and study treatment not permanently discontinued
COMD16A	Banned asthma related concomitant Medications used during the study*
Deviations leading to exclusion of data collected after occurrence of that event, from all analyses set	
WTH07A	Study procedures performed after withdrawing of informed consent

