- QMF149 150/80 microgram o.d. delivered via Concept1
- MF 200 microgram o.d. delivered via Twisthaler®

Randomized patients must have FEV_1 between 60% and < 90% of predicted normal at **both** Visit 101 and Visit 102 and they must qualify for treatment with low dose ICS plus LABA as per GINA 2016 guidelines. At Visit 102, **all** randomized patients must have $ACQ-7 \ge 1.5$. Refer to Section 4.1 Inclusion Criteria for ACQ-7 requirements.

Visit 102 (end of Run-in) and Visit 201(Randomization) must take place sequentially on the same day. The assessments at Visit 102 should be performed prior to administration of the first dose of study medication (Visit 201). Reversibility should NOT be done at Visit 102 (Table 6-1). Randomized patients will enter the 12-week Treatment epoch. All patients will receive both Concept1 and Twisthaler® inhalers (double-blind and double-dummy design). During the treatment epoch, patients will be instructed to inhale study medication once daily in the evening (between 5:00 pm and 8:00 pm).

[figure not shown]
Patients will be followed at regular intervals throughout the 12 week treatment epoch to assess the safety and efficacy of treatment, either by telephone or at clinic visits. Clinic visits are scheduled to take place after 4, and 12 weeks. All clinic visits should occur as scheduled per Table 6-1. Patients will be required to attend the clinic visits to perform trough measurements of lung function (24 hours post dosing) after the first dose of study medication (Visit 201) and after the dose of study medication administered at the clinic after 12 weeks of treatment (Clinic Visit 204). In case of logistical issues, Visit 204 (Week 12) should take place within a 4 day window. If this is not possible, the sponsor should be notified.

Pre-dose FEV_1 measurements will be assessed at Week 4. Telephone reviews of patients' status will be conducted after 8 weeks of treatment. Telephone contact with patients may indicate that a clinic visit is necessary, in which case an unscheduled clinic visit should be arranged as soon as possible and should include safety assessment (AEs, concomitant medications review and unscheduled laboratory exams as appropriate).

A final telephone contact must be conducted at 30-days after last treatment date (telephone Visit 301 or unscheduled visit safety call for patients who discontinue treatment earlier than 12 weeks).

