4.1 Inclusion criteria

Patients eligible for inclusion in this study must fulfill all of the following criteria:

- 1. Written informed consent must be obtained from all patients before any study-related assessment is performed. Patients below the legal age of consent are required to have the Parental Informed Consent signed by the patient's parent/legal guardian; adolescents are required to sign the Assent Form.
- 2. Male and female adolescents aged ≥ 12 to < 18 years old (depending upon regulatory and/or institutional Review Board (IRB)/Independent Ethics Committee (IEC)/REB approval and/or country participation) and male and female adults aged ≥ 18 years and ≤ 75 years old.
- 3. Patients with a documented diagnosis of asthma for a period of at least 3 months prior to Screening (Visit 1).
- 4. Patients who have used low dose ICS (Appendix 9), with or without another controller therapy (i.e., LABA, Leukotriene Receptor Antagonist (LTRA)) at stable dose for at least 1 month prior to Screening (Visit 1).
- 5. Adult patients must be symptomatic despite treatment with existing therapy. Patients must have ACQ-7 score ≥ 1.5 at Visit 101 and at Visit 102 (i.e., inadequately controlled).
- 6. Adolescent patients:
 - If taking low dose ICS (without LABA), patients must be symptomatic despite treatment with low doses of ICS. These patients must have ACQ-7 score \geq 1.5 at Visit 101 and at Visit 102 (i.e., inadequately controlled).
 - If taking low dose ICS / LABA, patients may be included only if ACQ-7 score ≥ 1 and <1.5 at Visit 101 (i.e., adequately controlled). However, ACQ-7 score must be ≥ 1.5 at Visit 102, directly prior to randomization.
- 7. Pre-bronchodilator $FEV_1 \ge 60\%$ and < 90% of the predicted normal value for the patient according to ATS/ERS criteria after withholding bronchodilators at both Visits 101 and 102.
 - Withholding period of bronchodilators prior to spirometry: SABA for ≥ 6 hours and FDC or free combinations of ICS/LABA* for ≥ 48 hours (14 days for once daily combinations, i.e., indacaterol), short acting anticholinergies (SAMA) for ≥ 8 hours, xanthines ≥ 7 days.

*In case of combination ICS/LABA, ICS should be continued.

Washout period of each drug should be kept as close as possible as above and should not be longer. If washout period is considered to be longer, please contact your Novartis Medical Monitor.

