## 2.2 Analysis sets

The following analysis sets are defined:

- The randomized (RAN) set will consist of all patients who were assigned a randomization number, regardless of whether or not they actually received study treatment. Patients in RAN will be analyzed according to the treatment they were randomized to. The RAN set will be used for a summary of patient disposition, demographics and baseline characteristics.
- The Full Analysis Set (FAS) will consist of all patients in the RAN set who received at least one dose of study treatment. Following the intent-to-treat principle, patients will be analyzed according to the treatment they were assigned to at randomization. The FAS will be used in the analysis of all efficacy variables.
- The Per-Protocol set (PPS) will include all patients in the FAS who did not have any major protocol deviations. The list of major protocol deviations will be available in [Appendix 6.7](#) prior database lock. Patients will be analyzed according to the treatment they received. The PPS will be used for supportive analysis of the primary analysis only.
- The Safety Set will consist of all patients who received at least one dose of study treatment including non-randomized patients who received study treatment in error. Patients will be analyzed according to the treatment they received. If patients switch double-blind treatment during the study, they will be counted and analyzed only once according to their initial treatment. The safety set will be used in the analysis of all safety variables.

•

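### SAP deviation INCL07A, read plainly, removes a patient from the per-protocol set only if FEV1 is out of range at both Visits 101 and 102, although failing at either visit makes the patient ineligible

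*SAP*

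**What the plan says.** **Eligibility.** Protocol section 3.1 requires randomized patients to have FEV1 "between 60% and < 90% of predicted normal at both Visit 101 and Visit 102". Inclusion criterion 7 in section 4.1 sets the same limits, with a lower bound of 60% and an upper bound worded "< 90% of the predicted normal value for the patient according to ATS/ERS criteria after withholding bronchodilators at both Visits 101 and 102". It allows one repeat at each visit.

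**Per-protocol exclusion.** SAP section 2.2 says that the PPS "will include all patients in the FAS who did not have any major protocol deviations" and points to the list in section 6.7. There, INCL07A describes pre-bronchodilator FEV1 under 60%, or 90% and over, "of predicted normal after withholding bronchodilator both at visit 101 and 102".

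**Neighbouring rows.** Two ACQ-7 rules in the same table also turn a two-visit criterion into a deviation. INCL05A reads "Adult patients with ACQ-7 score < 1.5 at visit 101 and/or visit 102". INCL06A covers adolescents on ICS without LABA who "have ACQ -7 < 1.5 at visit 101 and/or visit 102".

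**Use of the set.** SAP section 2.2: "The PPS will be used for supportive analysis of the primary analysis only". Section 2.5.4 gives its purpose as estimating the effect in patients who adhered to the protocol.

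**The concern.** When a criterion must hold at two visits, it is broken by failure at either one. INCL07A reverses the FEV1 range but keeps the word *both*. Read as it stands, it therefore describes a patient who failed twice. A patient out of range once, even at Visit 102 on the day of randomization, would not meet the description and would count as a protocol adherer on this point.

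At stake is who belongs to the PPS. Its only analysis has trough FEV1 as the outcome, and pre-bronchodilator FEV1 is the eligibility variable closest to that outcome. The table also treats the two measures differently without giving a reason: missing the ACQ-7 threshold once removes an adult, while missing the FEV1 range once, on the plain reading, does not.

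The plan allows for such patients being randomized. SAP section 2.3.2 keeps baseline categories below 60% and at or above 90% of predicted for protocol deviations.

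**Working it through.** **1. The plan's own figures, to see whether they depend on this rule.** Inputs from SAP sections 1.1 and 3: 338 completers per arm, two-sided 5% level, FEV1 difference 100 mL with SD 380 mL, ACQ-7 difference 0.18 with SD 0.80. Power is approximately Φ(δ / (SD × √(2/n)) − 1.96), and √(2/338) = 1/13.

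- FEV1: 100 / (380/13) = 3.42, so power is Φ(1.46) = 92.8%, against the stated 93%.
- ACQ-7 alone: 0.18 / (0.80/13) = 2.925, so power is Φ(0.965) = 83.3%. Multiplied by the FEV1 power, 0.928 × 0.833 = 77.3%, against the stated 77%.

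Both figures reproduce. PPS membership enters neither, so a change to INCL07A leaves them as they are.

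**2. The rule against the criterion.** Eligible means in range at 101 and in range at 102. The complement is out of range at 101 or at 102.

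| Visit 101 | Visit 102 | Eligible (protocol) | Flagged, plain reading of INCL07A | Flagged with *and/or* |
|---|---|---|---|---|
| in | in | yes | no | no |
| out | in | no | **no** | yes |
| in | out | no | **no** | yes |
| out | out | no | yes | yes |

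The plain reading catches one of three ineligible patterns; *and/or* catches all three. This counts patterns, not patients.

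**3. Whether another code catches the missed patterns.** INCL08A to INCL08C concern reversibility and the ATS/ERS spirometry criteria. No other row in section 6.7 refers to the percent-predicted range. A patient missed by INCL07A leaves the PPS only if some unrelated deviation applies.

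**4. The alternative reading.** Criterion 7 ends "for the patient according to ATS/ERS criteria after withholding bronchodilators at both Visits 101 and 102". INCL07A echoes that ending, so *both* may belong to the withholding of bronchodilators. The rule then gives no visit at which FEV1 must be out of range, and whoever programs the PPS has to choose.

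**5. How many patients.** The documents give no rate, so what follows is an assumption shown as a range. Let p be the proportion of randomized patients out of range at each visit, and φ the between-visit correlation of that status. Then

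- P(out at both) = p² + φp(1 − p)
- P(out at exactly one) = 2p(1 − p)(1 − φ)

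| p | φ | Exactly one visit, of 750 | Share of ineligible patients missed |
|---|---|---|---|
| 2% | 0 | 750 × 0.0392 = 29.4 | 0.0392 / 0.0396 = 99% |
| 2% | 0.9 | 750 × 0.00392 = 2.9 | 18% |
| 5% | 0 | 750 × 0.095 = 71.2 | 97% |
| 5% | 0.9 | 750 × 0.0095 = 7.1 | 17% |

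The result runs from about 3 to about 71 patients, driven wholly by the assumed p and φ. It shows only that the number cannot be settled from the documents.

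**The case against.** The strongest reply is that INCL07A is careless copying and not a narrower rule. It follows criterion 7 closely: the drafter seems to have reversed the range and left the closing phrase alone. It also carries the number of criterion 7, so a reader could take it to mean simply that criterion 7 was not met, which covers failure at either visit.

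A reader might infer from *and/or* in INCL05A and INCL06A that *both* in INCL07A is a deliberate restriction. The documents do not support going that far, because section 6.7 is loosely worded elsewhere. EXCL11A counts from Visit 1 where protocol exclusion 11 counts from Visit 101; EXCL34A counts from Visit 101 where exclusion 34 counts from Visit 1. INCL08A, read alone, would flag patients whom criterion 8 admits on historical evidence. The contrast with the ACQ-7 rows favours the plain reading but does not prove intent.

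It can also be said that few such patients should exist. Criterion 7 allows a repeat, the site contacts the IRT only after confirming all criteria (protocol 5.3), and monitoring verifies adherence to the eligibility criteria in full (protocol 8.1). Deviations are tabulated by category (SAP 2.3.1), so some of these patients would be visible in the report.

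Much of this stands: intent is unknown, the number may be small, and the effect is limited. None of it makes the text correct. On one reading the rule contradicts eligibility; on the other it leaves the visit unspecified. Neither states the rule that the protocol implies.

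**Conclusion.** Wrong as written, and minor. The plain reading of INCL07A covers one of three ineligible visit patterns; the alternative reading does not say which visit counts. Patients randomized despite failing at exactly one visit, after any permitted repeat, could therefore stay in the PPS.

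Two stronger conclusions should be resisted. A reader might infer that ineligible patients will certainly be in the PPS. That would require such patients to have been randomized and the code to have been applied literally, and the documents show neither. A reader might also infer that the trial's result is at risk. It is not: the primary and key secondary tests use the FAS, so type I error, power and the confirmatory conclusion do not depend on this row. Only the supportive PPS analysis of trough FEV1 does.

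The finding rests on the text of the two documents. It needs no assumed rate; the patient counts shown above do.

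**What to change.** Reword INCL07A before database lock, which is when protocol section 9.1 requires major deviations to be settled:

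*Pre-bronchodilator FEV1 < 60% or >= 90% of predicted normal, after withholding bronchodilator, at Visit 101 and/or Visit 102 (after any permitted repeat).*

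This keeps the withholding condition of criterion 7, matches the form of INCL05A and INCL06A, and makes clear that a patient who passes on the allowed repeat is not a deviator. If the intention was always failure at either visit, the edit only makes the text say so.

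The cost is one phrase in the SAP table and the matching line in the PPS derivation. The PPS may be slightly smaller. No sample size, power or FAS analysis changes.

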• A one-time repeat of percent predicted FEV₁ (pre-bronchodilator FEV₁) is allowed at Visit 101 as well as at Visit 102. Repeat of Visit 101 spirometry should be done in an ad-hoc visit to be scheduled on a date (preferably within 5 days of original Visit 101) that would provide sufficient time to receive confirmation from the spirometry data central reviewer of the validity of the assessment before randomization. Run-in medication should be dispensed only once the repeat spirometry was qualified by spirometry equipment, if all inclusion at Visit 101 are successful in case of necessary repeat of Visit 101.

A one-time re-screen is allowed in case the patients fail to meet the criteria at the repeat, provided the patients return to their previous treatment until re-screened. In this circumstance, patients are not required to go back on prior medication for 1 full month duration as outlined in inclusion criterion 4.

- 8. Patients who demonstrate an increase in FEV₁ of \geq 12% and \geq 200 mL within 15 to 30 minutes after administration of 400 microgram salbutamol / 360 microgram albuterol (or equivalent dose) at Visit 101. Spacers may be used for reversibility testing.
 - All patients must perform a reversibility test at Visit 101.

If reversibility is not demonstrated at Visit 101:

- Reversibility should be first repeated once.
- If the retest does not show reversibility, patients may be permitted to enter the study with documented historical evidence of reversibility that was performed according to American Thoracic Society (ATS) / European Respiratory Society (ERS) guidelines within 2 years prior to Visit 1.
- Alternatively, patients may be permitted to enter the study with a historical positive broncho-provocation test that was performed within 2 years prior to Visit 1.

If reversibility is not demonstrated at Visit 101 (or after repeated assessment at ad-hoc visit) and historical evidence of reversibility / broncho-provocation not available (or not performed according to ATS/ERS guidelines) patients will be noted as screen failure.

Spacer devices are ONLY permitted during reversibility testing. The decision whether or not to use a spacer for the reversibility testing will be taken by the study investigator.

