Women are considered post-menopausal and not of child-bearing potential if they have had 12 months of natural (spontaneous) amenorrhea with an appropriate clinical profile (e.g., age appropriate, history of vasomotor symptoms) or have had surgical bilateral oophorectomy (with or without hysterectomy), total hysterectomy, or tubal ligation at least six weeks ago. In the case of oophorectomy alone, only when the reproductive status of the woman has been confirmed by follow-up hormone level assessment is she considered not of child-bearing potential.

If requested by local authorities/ethics committees, additional and more frequent pregnancy testing might be performed.

34. Use of Long Acting Muscarinic Antagonist (LAMA) within 3 months prior to Visit 1.

5 Treatment

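### The reversibility exclusions for the per-protocol set in SAP 6.7 leave out an entry route that protocol criterion 8 allows, and two other rows count from a different visit than the protocol

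*SAP*

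**What the plan says.** **Where the list gets its force.** Protocol 9.1 defers the definition of major deviations to the SAP. SAP 2.2 defines the PPS as FAS patients without a major deviation and points to SAP 6.7 for the list. SAP 2.5.4 uses the PPS to estimate the effect in patients who adhered to the protocol. SAP 2.2 restricts it to supporting the primary analysis.

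**Reversibility, SAP 6.7.** Two rows stand under the heading for exclusion from the PPS. INCL08A reads "Patients for whom increase in FEV1 < 12% and/or < 200 ml within 30 minutes after administration of 400 microgram salbutamol/360 microgram albuterol" (or an equivalent dose) at Visit 101. INCL08B reads "Patient has not achieved an acceptable spirometry result does not have historical reversibility".

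**Reversibility, protocol 4.1, criterion 8.** A patient not reversible at Visit 101 is retested once. If the retest also fails, "patients may be permitted to enter the study with documented historical evidence of reversibility" obtained within the 2 years before Visit 1. The alternative is "a historical positive broncho-provocation test that was performed within 2 years prior to Visit 1". Failure at Visit 101 or on retest leads to screen failure only with this added condition: "historical evidence of reversibility / broncho-provocation not available (or not performed according to ATS/ERS guidelines) patients will be noted as screen failure".

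**Look-back rows.** For LAMA, EXCL34A has "LAMA taken less than 3 months prior to Visit 101" and protocol criterion 34 has "Use of Long Acting Muscarinic Antagonist (LAMA) within 3 months prior to Visit 1". For investigational drugs, EXCL11A begins "Other investigational drugs used within 30 days of visit 1", whereas protocol criterion 11 and Table 5-2 count back from Visit 101.

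**The concern.** An analysis meant to describe adherers should not drop patients who entered by a route the protocol permits. INCL08A names one test at one visit and carries no exception. INCL08B brings in historical reversibility but not broncho-provocation, and the SAP does not say how the two rows combine. Who is in the PPS then depends on how the rows are programmed.

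The look-back rows raise a smaller issue of the same kind. EXCL11A reaches further back than criterion 11, so it can flag someone who was eligible. EXCL34A reaches less far back than criterion 34, so it can leave in someone who was not.

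What is at stake is the membership and the description of one supportive analysis set.

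**Working it through.** The plan states no figure on this point, so there is none to reproduce. The check compares the rows with the criteria.

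**1. Reversibility.** Criterion 8 gives four yes/no items: Visit 101 test (V), repeat test (R), historical reversibility (H) and historical positive broncho-provocation (B). That makes 2^4 = 16 combinations. Criterion 8 is met if at least one is yes, so 16 − 1 = 15 combinations are eligible.

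| Reading of the rows | Flag raised when | Eligible combinations flagged |
|---|---|---|
| INCL08A on its own, Visit 101 test only | V is no | 2^3 − 1 = 7 |
| INCL08A on its own, repeat counted as part of Visit 101 | V and R are no | 2^2 − 1 = 3 |
| INCL08A waived by a repeat or by historical reversibility | V, R and H are no | 2^1 − 1 = 1 |

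The one combination left under the most lenient reading is broncho-provocation as the sole evidence. These are counts of logical combinations, not of patients. They show only that no reading of the two rows reproduces criterion 8.

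**2. Look-back rows.** Protocol Table 6-1 puts Visit 1 at Day −35 to −21 and Visit 101 at Day −21. Protocol 3.1 caps screening at 2 weeks and allows it to be shorter. The gap g between the two visits is therefore 0 to 14 days. I take 3 months as about 91 days (assumption); the size of the shift does not depend on it.

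| g (days) | Criterion 34 opens: −21 − g − 91 | EXCL34A opens: −21 − 91 | Days missed | Criterion 11 opens: −21 − 30 | EXCL11A opens: −21 − g − 30 | Days over-flagged |
|---|---|---|---|---|---|---|
| 14 | −126 | −112 | 14 | −51 | −65 | 14 |
| 7 | −119 | −112 | 7 | −51 | −58 | 7 |
| 0 | −112 | −112 | 0 | −51 | −51 | 0 |

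Measured from Visit 101, EXCL11A looks back 30 + g days: 44, 37 or 30, against 30 in criterion 11. If the 5-half-life limb is the longer one, the shift is still g days. Both mismatches disappear only when Visits 1 and 101 fall on the same day.

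**3. Is there a common convention?** Neighbouring rows keep the protocol's reference visit: INCL03A and EXCL01A use Visit 1; EXCL21A, COMD09A and COMD10A use Visit 101. EXCL34A and EXCL11A depart from the protocol in opposite directions, so no single convention explains both.

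**The case against.** The best counter-argument starts from the definition. The PPS drops patients with major protocol deviations, and someone admitted by a route that criterion 8 permits has no deviation. The rows would then be short labels with the protocol wording behind them. That may well be the intention. But the protocol hands the definition to the SAP, and the SAP hands it to this table, which is introduced as covering deviations and other criteria that lead to exclusion. I found no sentence saying that the protocol wording prevails. One caution: in the text I read, a figure before the table is not shown and the footnote to COMD16A does not appear. A note there could settle the matter.

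Three further objections have force.

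- **Separate application is the less natural reading.** If INCL08A alone removed everyone negative at Visit 101, the mention of history in INCL08B would do little work. I accept this. It reduces the problem to broncho-provocation but does not remove it.
- **EXCL34A may be a deliberate choice.** The SAP may decide which breaches count as major, and the list is plainly selective: it has no row for exclusion criteria 9, 10 or 13, for example. Keeping some violators is therefore not in itself an error. This does not help INCL08A or EXCL11A, which flag patients who breached nothing.
- **Eligibility is checked before randomization** (protocol 5.3), so a patient randomized in breach of criterion 34, with last use inside a slice of at most 14 days, should be rare.

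A reader might also infer an undeclared departure from the protocol, because SAP section 4 lists only the added ACQ-5 analyses. The documents do not support that. Section 4 concerns analyses the protocol specified, and the protocol specified no list of major deviations.

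**Conclusion.** The point holds, and it is minor. Read as written, SAP 6.7 removes from the supportive PPS patients validly admitted on a historical positive broncho-provocation test, and on a separate reading of the rows also those admitted on historical reversibility. This is the main finding, and it survives the most lenient reading.

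The look-back mismatches are secondary. Each is 0 to 14 days wide and probably affects few patients. EXCL11A can flag an eligible patient. EXCL34A can miss a violator, which may be intended.

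A reader might go on to infer a biased PPS result, a material loss of PPS size or a loss of power. None of these can be shown: neither document says how many patients entered by the historical routes or fall in the gaps. Nor can the day counts be turned into a share of patients. The primary analysis is on the FAS, so it, the type I error and the sample size are untouched.

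The conclusion assumes that the rows are applied as worded. Which reference visit is right for LAMA or investigational drugs is not judged here; the passages need to be reconciled.

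**What to change.** Before database lock:

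1. Merge INCL08A and INCL08B into one flag, raised only when no route in criterion 8 is met: the Visit 101 test or its permitted repeat, historical reversibility, or a historical positive broncho-provocation test, each under the conditions the protocol sets.
2. Reconcile the reference visits of EXCL34A and EXCL11A with criteria 34 and 11, or add a sentence saying that the difference is intended.

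The cost is four rows in one appendix table and the matching deviation flags. It needs no new data and leaves the primary analysis unchanged.
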